### **VERSION 2.0 LETTER OF AMENDMENT #1**

DATE: February 18, 2022

TO: ACTG CTU Principal Investigators, CRS Leaders, and CTU/CRS Coordinators

FROM: A5379 Protocol Team

SUBJECT: Letter of Amendment #1 for Version 2.0 Protocol A5379

The following information affects the A5379 study and must be forwarded to the institutional review board (IRB)/ethics committee (EC) responsible for oversight of the study as soon as possible for their information and review. This Letter of Amendment (LOA) must be approved by the IRB/EC before implementation.

The following information affects the Sample Informed Consent. Your IRB/EC is responsible for determining the process of informing participants of the contents of this LOA.

Upon receiving final IRB/EC and any other applicable regulatory entity approvals for this LOA, sites should implement the LOA immediately. Sites are still required to submit an LOA registration packet to the DAIDS Protocol Registration Office (PRO) at the Regulatory Support Center. Sites will receive a registration notification for the LOA once the DAIDS PRO verifies that all required LOA registration documents have been received and are complete. A copy of the LOA registration notification, along with this letter and any IRB/EC correspondence, should be retained in the site's regulatory file.

This LOA is being implemented for the following reasons:

- To correct blood volumes listed in the sample informed consent.
- To note that trained study staff may administer the study vaccination.
- To add that changes in ART in the 28 days prior to study entry are allowed unless the change is due to ART toxicity.
- To add inactive or resolved cutaneous Kaposi sarcoma as an exception to exclusion criterion 4.4.7.
- To add that receipt of flu vaccine within 14 days prior to study entry is allowed.
- To add a complete history of COVID-19 vaccines to medication history.
- To allow remote data collection of post-entry evaluations due to illness or quarantine.
- To describe that COVID-19 vaccines are not prohibited on study.
- To clarify that pregnancy testing results must be negative within 2 days prior to the participant receiving study vaccine.
- To remove pregnancy testing at screening.
- To change "regardless of grade" to "Grade ≥1" for the following:
  - a. Any concomitant medication associated with Grade ≥1 local and systemic injection reactions within 7 days after any study vaccine injection must be recorded on the eCRF.
  - b. All Grade ≥1 local and systemic injection reactions within 7 days of any study vaccine injection must be recorded on the eCRF.
- To add a paragraph in Appendix I, Sample Informed Consent (WHAT ABOUT CONFIDENTIALITY?)
   now that the SDAC work in the ACTG is also covered by an approval from the Advarra IRB.
- To update language in Appendix I, Sample Informed Consent (WHAT HAPPENS IF I AM INJURED?)
- To add agreed-upon language from the ACTG Leadership Steering Committee in ATTACHMENT B, CONSENT FOR USE OF SAMPLES IN OTHER STUDIES.

Page 2 of 14

• To update the Protocol Team Roster and Study Management sections.

**ACTG Laboratory Center at UCLA (ALC-UCLA)** 

[name]

[name] [contact]

Email: [contact]

3. Study Management

[name] was added to the second and third bullet points under subsection Data Management:

Page 6 of 14

- For transfers, reference the Study Participant Transfer SOP 119, and contact [name] and [name] directly.
- For other questions, send an e-mail message to [contact] (ATTENTION: [name] and [name]).
- 4. Inclusion Criterion 4.1.2

The criterion was updated as shown below:

4.1.2 On current-HIV-1 antiretroviral therapy (ART) for >56 days immediately prior to study entry.

NOTE: Changes to ART due to ART toxicity in the 28 days prior to study entry is not allowed. For questions related to ART toxicity, sites should contact the team per the Study Management section. Individuals must not have changed ART within 56 days prior to study entry except for changes in integrase inhibitors, which will be allowed.

5. Exclusion Criterion 4.4.7

The criterion was updated as shown below:

- 4.4.7 Cancer diagnosis within 5 years prior to study entry, other than squamous or basal cell carcinoma of the skin **and resolved or inactive cutaneous Kaposi sarcoma**.
- 6. Exclusion Criterion 4.4.16

The criterion was updated as shown below:

4.4.16 Receipt of any inactivated virus vaccine within 14 days prior to study entry.

NOTE: Receipt of flu vaccine within 14 days prior to study entry is allowed.

### 7. 5.3.1 HEPLISAV-B

Study clinician was replaced with study staff in items 3 and 5 as shown below:

- 3. The center seals of the vials will be removed, and the vial stoppers wiped with an alcohol wipe prior to insertion of a sterile needle attached to a sterile syringe. The study **staff** clinician will determine the needle size depending upon the participant's deltoid muscle size.
- 5. For the prefilled syringes, attach a sterile needle and administer intramuscularly. The study **staff** clinician will determine the needle size depending upon the participant's deltoid muscle size. HEPLISAV-B should be administered as soon as possible. HEPLISAV-B can be kept at room temperature (20°C-25°C) for up to 8 hours but exposure time to room temperature should be minimized.

IND Number: 019394 Page 7 of 14

#### 8. 5.3.2 ENGERIX-B

Study clinician was replaced with study staff in items 3 and 5 as shown below:

- 3. For the vials, remove the center seals of the vials and wipe the vial stoppers with an alcohol wipe prior to insertion of a sterile needle attached to a sterile syringe. The study **staff** clinician will determine the needle size depending upon the participant's deltoid muscle size.
- 5. For the prefilled syringes, attach a sterile needle and administer intramuscularly. The study **staff** clinician will determine the needle size depending upon the participant's deltoid muscle size. ENGERIX-B should be administered as soon as possible. ENGERIX-B can be kept at room temperature (20°C-25°C) for up to 72 hours but exposure time to room temperature should be minimized.

## 9. 5.5.2 Prohibited Medications

Clarification about COVID-19 administration was added as shown below:

HBV vaccine preparations other than study vaccines HEPLISAV-B and ENGERIX-B are prohibited. Standard-of-care (SOC) vaccines, including COVID-19 vaccines, will be permitted during the conduct of this study. If administration of a COVID-19 vaccine occurs after study entry and near the 2nd or 3rd study vaccine dose, adjust the 2nd or 3rd dose of the study vaccine to avoid immediate overlap reactogenicity; however, it is not prohibited to give them together, and this is at the discretion of the site investigator. If an SOC vaccine and/or COVID-19 vaccine is administered on the same day as the study-provided vaccine, use different arms. Refer to the A5379 PSWP for further details about COVID-19 vaccines and this study.

#### 10. Table 6.1-1 Group A (Arm 1 only)

Pregnancy testing at screening was removed as shown below:

Evaluations	Screening	Entry (Day 0)		Po		Premature Study				
			4	8	12	24	28	52	72	Discontinuation
Visit Windows	Within 45 days	≥24 hours after screening	-4/+7 days	+ / da				±14	days	Evaluations (*refer to section 6.2.4)
Pregnancy Testing	X	X	X						Χ	X

# 11. Table 6.1-2 Group A (Arms 2 and 3 only)

Pregnancy testing at screening was removed as shown below:

Evaluations	Screening	Entry (Day 0)	,		3		Pos	st-Er	ntry I (We			ons		
		(Day 0)	Evaluation	4	8	12	24	28	32	48	72	Premature		
Visit Windows	Within 45 days	≥24 hours after screening	≥16 to ≤28 hours post 1 st vaccination; at US sites only and is optional	-4/+7 days		±7	7 da .	ys			14 nys	Study Discontinuation Evaluations (*refer to section 6.2.4)		
Pregnancy Testing	X	Χ		Χ			Χ				Χ	X		

# 12. Table 6.1-3 Group B Only

Pregnancy testing at screening was removed as shown below:

Evaluations	Screening	Entry	F	os	t-En	Premature					
		(Day 0)	4	8	12	24	28	32	48	72	Study Discontinuation
Visit Windows	Within 45 days	≥24 hours after screening	-4/+7 days		±7	ˈdaː̯	ys		±14	days	Evaluations
Pregnancy Testing	X	X	Χ			Χ				Χ	X

# 13. Table 6.3.3-1 Medication History

"COVID-19 vaccines" was added:

Table 6.3.3-1: Medication History

rable didio in Medication Filetory	
Medication Category	Complete History or Timeframe
Antiretroviral therapy	Within 60 days prior to entry
HBV vaccination1	Complete history
Immune-based therapy	Within 1 years prior to entry
Blinded study treatment	Within 1 years prior to entry
HIV-1-related vaccines	Within 1 years prior to entry
COVID-19 vaccines	Complete History
Prescription drugs for treatment of opportunistic infections	Within 60 days prior to entry

IND Number: 019394 Page 9 of 14

Medication Category	Complete History or Timeframe
Prescription drugs for prophylaxis of opportunistic infections	Within 60 days prior to entry
Prescription drugs (other)	Within 45 days prior to entry
Herbal/dietary supplements	Within 45 days prior to entry
Sex-hormone medications or sex-	Within 1 year except as noted below
hormone analogues or antagonists2	

## 14. 6.2.3 Post-Entry Evaluations

The following was added under the Missed Vaccination Visits section:

### **Remote Data Collection**

Study visits may be conducted remotely (e.g., telephone, telehealth) in the following situations:

- A participant is unable to attend a visit because of illness, lockdown status, or quarantine; the site must inform the CMC ([contact])
- The site is temporarily unable to conduct non-essential visits in the clinic; the site must inform the CMC ([contact])

Remote visits should be conducted during the visit window according to the SOE. Regardless of the situation, sites should document which visits were conducted remotely. For visits that are conducted remotely, the site should attempt to obtain as much of the visit-specific required information based on the SOE as possible and record it on the relevant eCRF.

In addition to the remote visit, the participant should be scheduled for an in-person visit for all evaluations that were not conducted at the remote visit. If the in-person visit evaluations are outside of the visits window, have the participant in as soon as possible for safety-related evaluations as an unscheduled visit, but if within a week of the next scheduled visit window, then wait for the next scheduled visit and add any safety lab evaluations not already being performed. If the participant is unable or prefers not to come to the site for a visit, priority safety labs are permitted to be done at a local lab or as part of the standard of care. Record these on an eCRF. The priority safety labs include: chemistry, hematology, and liver function tests.

We ask the sites to prioritize sample collection for HBsAb testing at Week 12 for Arm 1 in Group A, and Week 28 for Arms 2 and 3 in Group A and for Group B. If there is a need to limit in-person interactions at the site, the in-person component can be restricted to the blood draw, and the remaining visit evaluations can be completed remotely.

### 15. 6.3.4 Clinical Assessments

- a. A bullet point was added after "Inactivated or live virus vaccine" under the Concomitant Medications section as shown below:
  - Vaccines (experimental or standard of care, including COVID-19 vaccines and COVID-19 booster vaccines)

Page 10 of 14

b. The last bullet point under the Concomitant Medications section was updated as shown below.

Any concomitant medication associated with Grade ≥1 local and systemic injection reactions regardless of grade, within 7 days after any study vaccine injection.

### 16. 6.3.5 Laboratory Evaluations

Changes were made in the second and third sentences under Pregnancy Testing as shown below:

Pregnancy testing must occur on the day of vaccination and the results must be negative within 2 days prior to the participant receiving HEPLISAV-B or ENGERIX-B. Post-entry, **nN**ote that a subsequent pregnancy test is not required for pregnant participants who consented to continue with the study.

17. 7.2 Adverse Event Collection Requirements for This Protocol

The fourth bullet point in the first paragraph of this section was updated as shown below:

- All Grade ≥1 local and systemic injection reactions within 7 days of any study vaccine injection regardless of grade.
- 18. APPENDIX I: SAMPLE INFORMED CONSENT, "WHAT DO I HAVE TO DO IF I AM IN THIS STUDY?"

The blood collection amounts under Screening, Entry, and Other Study Visits have been updated as follows:

Screening: The fifth bullet point has been revised to read:

You may have approximately 34-42 mL (about 2-3 tablespoons) of blood collected

Entry: The third bullet point has been revised to read:

You may have approximately 461-135 mL (about 11-9 tablespoons) of blood collected

Other Study Visits: The second bullet point has been revised to read:

You will have as little as 3-5 mL (about 1 teaspoon) to as much as 27-132 mL (2-9 tablespoons) of blood collected at any one visit

IND Number: 019394 Page 11 of 14

rage II oi i

19. APPENDIX I: SAMPLE INFORMED CONSENT, "WHAT DO I HAVE TO DO IF I AM IN THIS STUDY?"

The third bullet point under Other Study Visits has been updated as follows:

- If you are able to become pregnant, you will have a pregnancy test and the result must be negative within 2 days prior to receiving a study vaccine dose. You will also have a pregnancy test during the visits when you receive the vaccine and at your last study visit. Options about staying on the study if you become pregnant, are explained elsewhere in the consent.
- 20. APPENDIX I: SAMPLE INFORMED CONSENT, "WHAT DO I HAVE TO DO IF I AM IN THIS STUDY?"
  - a. The following bullet point was removed under Screening as shown below:
    - If you are able to get pregnant, some of your blood or urine will be collected to test for pregnancy. If the pregnancy test is positive, you will not be able to join the study.
  - b. The following was added under Other Study Visits as shown below:

	4.6.1	Analysis Sets for 4.5.1 - 4.5.5	. 19
	4.6.2	Details on Outcome Measures for 4.5.1 – 4.5.5	. 19
	4.6.3	Handling of Missing Data for 4.5.1 - 4.5.5	. 19
5	ANALYSIS	CONSIDERATIONS	20
	5.1 Gene	ral Considerations	20
	5.2 Analy	/sis Approaches	20
	5.2.1	Group A Primary:	. 20
	5.2.2	Group A Secondary:	. 21
	5.2.3	Group B Primary:	. 22
	5.2.4	Group B Secondary:	. 22
6	REPORT C	ONTENTS	23

Version History

Version	Changes Made	Date Finalized (mm/dd/yyyy)
1.0	Original Version	11/18/2019
1.1	Protocol amendment review (V1.0, LOA #1)	02/05/2020
3.0	 Protocol Version 2.0 "Post-injection reactions" was changed to "Grade ≥2 adverse events" throughout to reflect updates to protocol secondary objectives (#7 in Group A, #4 in Group B below). Subset analyses were added as Report Content 11. Minor text edits were made throughout for clarity. Protocol amendment review (V2.0, LOA #1): No changes 	08/19/2020 04/29/2022
	 related to the LOA. A new section was added to include descriptions of primary and key secondary estimands, guided by ICH E9(R1). Text edits were made in sections following the new section for clarification. Additional missing data considerations for sensitivity analyses were added. Additional details about the statistical analyses were added. 	
3.1	Protocol amendment review (V3.0)	01/06/2023

1 Introduction

1.1 Purpose

This Primary Statistical Analysis Plan (SAP) describes the A5379 primary and secondary outcome measures that will be included in the primary manuscript. They address the major primary and secondary objectives of the study. The Primary SAP outlines the general statistical approaches for the analysis of the study, including the interim analyses of the primary outcome. It has been developed to facilitate discussion of the statistical analysis components and to provide agreement among the study team members regarding the statistical analyses to be performed and presented in the Primary Analysis Report.

Detailed outlines of tables, figures, and coding descriptions that will be included in the Primary Analysis Report are provided in the Analysis Implementation Plan (AIP).

The Primary Analysis Report will be generated separately for Groups A and B in A5379, and the primary analysis timelines will be derived separately for Groups A and B. Analyses for the Primary Analysis Report for each Group will be finalized once the last participant in the Group has completed the Week 28 study visit (prior to study completion at Week 72), all queries have been resolved, and the study database closure/data lock has been completed.

Results from the primary analysis may be presented publicly, for example at a conference, upon completion of relevant data prior to the entire study database finalization.

The final analyses for the two study groups may be conducted at different times upon relevant study data finalization.

Outlines of analyses for other protocol objectives and outcome measures that are not included in the Primary SAP will be provided in separate SAPs.

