2.3.1 Primary Objectives

The comparison of SPR between Arms 1 and 3 will be conducted as non-inferiority. Such comparison between Arms 2 and 3 will be conducted as superiority.

Group A

- To compare the week 12 SPR of a two-dose regimen of HEPLISAV-B (Arm 1) versus the week 28 SPR of a standard three-dose regimen of ENGERIX-B (Arm 3) in hepatitis B virus (HBV) vaccine-experienced participants living with HIV.
- 2. To compare the week 28 SPR of a three-dose regimen of HEPLISAV-B (Arm 2) versus a standard three-dose regimen of ENGERIX-B (Arm 3) in HBV vaccine-experienced participants living with HIV.
- 3. To describe adverse events (AEs) reported in each study arm over the duration of the study.

Group B

- 1. To determine the week 28 SPR of a three-dose regimen of HEPLISAV-B in HBV vaccinenaïve participants living with HIV.
- 2. To describe AEs reported over the duration of the study.

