3.1 Primary Outcome Measures

3.1.1 Group A

- [For Primary Objectives 1 and 2] SPR defined as HBsAb ≥10 mIU/mL at 8 weeks after the two-dose series (at Week 12) in Arm 1 and at 4 weeks after the three-dose series (at Week 28) in Arms 2 and 3
- 2. [For Primary Objective 3] Reported AEs from study vaccination initiation to study discontinuation

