4.3 Primary Safety Estimands

4.3.1 Primary Objective 3 from Section 2.3.1 for Group A (Arm 1)

Estimand Description	Probability of adverse events over 72 weeks after the initiation of 2-dose regimen of HEPLISAV-B, in HBV vaccine-experienced adults living with HIV-1 who failed to achieve a protective level of antibodies against HBsAg.
Treatment	2-dose regimen of HEPLISAV-B
Target Population	HBV vaccine-experienced adults living with HIV-1 on ART who failed to achieve a protective level of antibodies against HBsAg, have suppressed HIV-1 RNA and CD4+ T-cell count ≥100 cells/mm³, and initiate 2-dose regimen of HEPLISAV-B vaccination series.
Variable	Occurrence of adverse event (AE) over 72 weeks after vaccine initiation.
Handling of Intercurrent Events	 Incomplete or delayed vaccine series: Participants with incomplete or delayed vaccine series are included. (Treatment Policy Strategy*) Pregnancy: Participants who become pregnant on study have the option of completing the vaccination series and the study. (Principal Stratum Strategy*) Death: Death is considered the worst graded event. (Composite Variable Strategy*)
Population-Level Summary	Proportion of participants.

4.3.2 Primary Objective 3 from Section 2.3.1 for Group A (Arm 2):

Description	Probability of adverse events over 72 weeks after the initiation of 3-dose regimen of HEPLISAV-B, in HBV vaccine-experienced adults living with HIV-1 who failed to achieve a protective level of antibodies against HBsAg.
Treatment	3-dose regimen of HEPLISAV-B
Target Population	HBV vaccine-experienced adults living with HIV-1 on ART who failed to achieve a protective level of antibodies against HBsAg, have suppressed HIV-1 RNA and CD4+ T-cell count ≥100 cells/mm³, and initiate 3-dose regimen of HEPLISAV-B vaccination series.
Variable	Occurrence AE over 72 weeks after vaccine initiation.

Handling of Intercurrent	Incomplete or delayed vaccine series: Participants with incomplete or delayed vaccine series are included. (Treatment Policy Strategy*)
Events	 Pregnancy: Participants who become pregnant on study have the option of completing the vaccination series and the study. (Principal Stratum Strategy*) Death: Death is considered the worst graded event. (Composite Variable Strategy*)
Population-Level Summary	Proportion of participants.

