4.4.2 Details on Outcome Measures for 4.3.1 – 4.3.4

All adverse events reported during the study will be included.

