4.4.3 Handling of Missing Data for 4.3.1 - 4.3.4

For participants who discontinue study prior to Week 72, assume no additional adverse events occur after loss to follow-up. A sensitivity analysis may be conducted where censoring occurs at the last study visit to estimate proportion using a time-to-event method.

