5.2 Analysis Approaches

5.2.1 Group A Primary:

- For each of the two primary objectives on vaccine response, the primary outcome measure on the SPR will be analyzed as a binary variable.
- A score-based approach similar to the Wilson method for a SPR proportion difference will be used to estimate a stratified confidence interval, known as Newcombe method (Yan

- and Su, 2010). Four strata will be defined by sex at birth and screening diabetes status, and the strata will use Mantel-Haenszel weights (Mantel and Haenszel. 1959).
- Non-inferiority comparison between Arms 1 and 3: For the final analysis, a two-sided 97.5% confidence interval will be provided for the estimated proportion difference between Arm 1 and Arm 3 (Arm 3 minus Arm 1). If the resulting confidence interval lies entirely below the non-inferiority margin of 10%, then non-inferiority of Arm 1 compared to Arm 3 (control) will be concluded. Superiority of Arm 1 compared to Arm 3 will be concluded if the confidence interval lies entirely below zero.
- Superiority comparison between Arms 2 and 3: For the final analysis, a two-sided 97.5% stratified confidence interval will be provided for the proportion difference between Arm 2 and Arm 3 (Arm 2 minus Arm 3). A repeated confidence interval approach according to the realized Lan and DeMets implementation of the O'Brien-Fleming sequential stopping boundary that accounts for the repeated analyses due to interim efficacy monitoring will be provided. If the resulting confidence interval lies entirely above zero, then superiority of Arm 2 compared to Arm 3 (control) will be concluded.
- To address the study objectives on safety, the proportion of participants with AEs will be summarized with a two-sided 95% confidence interval in each study arm using the Wilson method, across stratification factors.

5.2.2 Group A Secondary:

- The secondary analyses on SPR will be conducted using a two-sided type I error rate of 2.5% without further correction for multiple analyses. This type I error was chosen to provide confidence intervals of widths comparable to the primary outcome analyses.
- The secondary objectives on the SPR comparisons will be addressed using the following analysis approach. A two-sided 97.5% confidence interval around the difference in proportions will be calculated using the Newcombe method. These will also be stratified confidence intervals, similar to the primary analysis approach.

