 - a. Listing of premature discontinuations of vaccination series with reasons. For premature discontinuations, the number of vaccines received will be provided.
 - b. Number and times of administered vaccines
- 7. Adverse events and deaths
 - a. Summary of all reportable AEs defined in Section 7.2 of the protocol by MedDRA system organ class (SOC) and preferred term (PT) and by grade.
 - b. Summary of the participants who died, including primary cause of death with weeks from study entry.
 - c. Listing and narratives of deaths.
- 8. Pregnancies
 - a. Listing and description of all available information related to pregnancy and outcome.
- 9. HIV-Related Summaries
 - a. CD4 cell count and changes from baseline at study visits
 - b. HIV-1 RNA at study visits
- 10. Analysis of Primary Outcome Measures

Group A Outcomes Described in Section 3.1.1:

a. Primary Objective 1 described in Section 2.3.1 will be addressed by estimating the difference between Arms 1 and 3 (Arm 3 minus Arm 1) in the proportions of participants who achieve SPR, using the approach described in Section 5.2.1.

- b. Primary Objective 2 described in Section 2.3.1 will be addressed by estimating the difference between Arms 2 and 3 (Arm 2 minus Arm 3) in the proportions of participants who achieve SPR, using the approach described in Section 5.2.1.
- c. Primary Objective 3 described in in Section 2.3.1 will be addressed by estimating the proportion of participants with reported AEs, using the approach described in Section 5.2.1.

Group B Outcomes Described in Section 3.1.2:

- a. Primary Objective 1 described in Section 2.3.1 will be addressed by estimating the SPR proportion, using the approach described in Section 5.2.3.
- b. Primary Objective 2 described in Section 2.3.1 will be addressed by estimating the proportion of participants with reported AEs, using the approach described in Section 5.2.1. In addition, descriptive tables summarizing the events and the number of participants experiencing the events will be provided by grade. For the descriptive tables, the worst graded event per participant over time will be used.

11. Analysis of Secondary Outcome Measures

Group A Outcomes Described in Section 3.2.1:

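### The primary AE proportion is defined over 72 weeks but sits in a report finalized after the last Week 28 visit, where it can only match or understate that target

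*SAP*

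**What the plan says.** **Timing.** SAP 1.1 states that the analyses for each Group's Primary Analysis Report "will be finalized once the last participant in the Group has completed the Week 28 study visit (prior to study completion at Week 72", once queries are resolved and the data are locked. It also mentions later final analyses, which may fall at different times for the two Groups, but assigns no estimand to them.

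**Content.** For Group A, Section 6 item 10 lists the safety objective among the report contents; it "will be addressed by estimating the proportion of participants with reported AEs". The Group B list has a matching entry.

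**Definition.** Four layers of the SAP set the observation period:

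- Objective (2.3.1, Group A): "To describe adverse events (AEs) reported in each study arm over the duration of the study".
- Outcome (3.1.1, and the same in 3.1.2): "Reported AEs from study vaccination initiation to study discontinuation".
- Estimand (4.3.1; 4.3.2 to 4.3.4 use the same 72 weeks): "Occurrence of adverse event (AE) over 72 weeks after vaccine initiation".
- Counting rule (4.4.2): "All adverse events reported during the study will be included".

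**Estimator.** In 5.2.1, "the proportion of participants with AEs will be summarized with a two-sided 95% confidence interval in each study arm using the Wilson method". Section 5.2.3 does the same for Group B.

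**Incomplete follow-up.** Section 4.4.3: "For participants who discontinue study prior to Week 72, assume no additional adverse events occur after loss to follow-up". A time-to-event estimate, censored at the last study visit, is named there only as an optional sensitivity analysis.

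**Analysis set.** Section 4.4.1 keeps only vaccinated participants who meet the eligibility criteria of the latest protocol.

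**The concern.** At the Week 28 cut the last entrant has about 28 of the 72 weeks observed. Anyone who entered less than 44 weeks before the last entrant is also short of Week 72, unless the lag to lock makes up the difference. Followed as written, the report holds a crude AE proportion over mixed follow-up of 28 to 72 weeks, while every definition of it in the SAP says 72 weeks or the whole study. The main rule in 4.4.3 speaks only of participants who discontinue, not of those still being followed.

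What is at stake is the absolute AE proportion in each arm. SAP 1.1 allows the primary results to be presented publicly before the whole database is final, so a reader who takes the figure at its definition would think AEs somewhat rarer than they are.

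**Working it through.** **Direction.** The proportion of a cohort with at least one AE cannot fall over time. For the same participants, the crude proportion at the cut is therefore at or below the proportion at Week 72. It is strictly below if any first AE falls after the cut.

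**Inputs from the SAP.** Minimum follow-up 28 weeks and target 72 weeks (1.1, 4.3); 187 per arm (2.4.1); 73 in Group B (2.4.2). The SAP states no expected AE proportion, so there is no plan figure to reproduce.

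**Assumptions.** Uniform accrual over E weeks. Lag L weeks from the last Week 28 visit to the AE cut-off. True 72-week risk 50%. A share s of the cumulative 72-week hazard has accrued by week 28+L, with constant hazard afterwards.

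**Accrual anchor, Group A.** Section 2.5.1 aims the first efficacy look at 40% or more of the post-series results. Those exist at week 28 + 0.4E. That is before accrual ends only if 28 + 0.4E < E, so E > 28/0.6 = 46.7. The look is itself conditional on enrolment, so this is a guide only. I used 47 to 156 weeks.

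**Share short of 72 weeks** (E at least 44 − L): (44 − L)/E. With L = 0 this is 44/47 = 94% down to 44/156 = 28%.

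**Points low.** Averaging over those who are short:

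shortfall = [(0.5^s − 0.5)/((1 − s) ln 2) − 0.5] × (44 − L)/E

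With L = 0:

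- 90% of hazard by Week 28: (0.5359 − 0.5)/0.0693 − 0.5 = 1.8 points among those short. Times 0.936 = 1.7; times 0.282 = 0.5.
- 75% by Week 28: (0.5946 − 0.5)/0.1733 − 0.5 = 4.6 points. Times 0.936 = 4.3; times 0.282 = 1.3.
- Constant hazard (s = 28/72): (0.7637 − 0.5)/0.4236 − 0.5 = 12.3 points. Times 0.936 = 11.5; times 0.282 = 3.5.

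| Points low, 50% true risk | 90% by Week 28 | 75% by Week 28 | Constant hazard |
|---|---|---|---|
| L = 0, E = 47 to 156 | 1.7 to 0.5 | 4.3 to 1.3 | 11.5 to 3.5 |
| L = 12, E = 47 to 156 | 0.9 to 0.3 | 2.2 to 0.7 | 5.8 to 1.8 |

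The 90% column is the likelier one, since all doses are scheduled by Week 24. With a true risk of 30% or 80% and L = 0, the 90% column becomes 1.2 to 0.4 or 1.6 to 0.5.

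Group B has no accrual anchor. At an illustrative 26 weeks of accrual with L = 0, everyone is short and the three figures are 2.5, 6.5 and 17.6 points.

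**Scale.** The Wilson 95% half-width at 50% is 7.1 points for n = 187 and 11.2 for n = 73.

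**Would the censored estimate help?** Simulation with 187 per arm, E = 52, L = 0 and 50% true risk: the crude proportion averages about 48.5%, 46.1% and 39.6% in the three cases, and the Kaplan-Meier estimate about 50% in each. Its standard error is 4.0 to 5.1 points, against 3.5 to 3.7 for the crude proportion. It works only where follow-up reaches Week 72: at E = 26 and L = 0 the longest follow-up is 28 + 26 = 54 weeks, so only the later analysis can answer.

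**The case against.** The strongest reply is that SAP 1.1 describes staged reporting: a report at the Week 28 lock, openly before study completion, then final analyses. A reader might infer that the SAP means to present the early figure as the 72-week result. No section says so, and labelling could be settled in the separate implementation plan, which is not among the documents. This stands as a limit on the point: the understatement applies only if the early figure is read as its stated estimand. It does not remove the point, because no section gives the 72-week estimand to the later analysis or gives the early figure a different definition.

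The size may also be small. AE collection rules are in Protocol Section 7.2, of which only one amended bullet is available here, so what is collected after Week 28 is unknown. Protocol Version 1.0 dates from October 2019, and the February 2022 letter still amends entry criteria and screening. That suggests long accrual, although the first enrolment date is not given. In the likelier hazard pattern the shortfall is well inside the confidence interval half-width. All of this stands.

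A reader might also infer that the Week 52 versus Week 72 comparisons in 4.5.3 and 4.5.4 would be run at the early lock on unequal data. The documents do not support that: 4.6.2 simply uses those visits, and no section places the analysis at this lock. What is missing is only a stated reporting time.

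**Conclusion.** The conflict is in the SAP's own text and should be fixed. Section 1.1 sets a cut before Week 72, Section 6 puts the AE proportion in the report, and four layers define that proportion over 72 weeks or the whole study. The direction is certain: at or below the 72-week value. The size is not known. For Group A, on the stated assumptions, it is about 0.3 to 1.7 points if 90% of the hazard falls by Week 28 (lag 0 to 12 weeks), and up to 11.5 points only under constant hazard with 47 weeks of accrual and no lag.

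The safety objectives are descriptive and the Group A arms share one calendar cut under 1:1:1 randomization. No test changes and the comparison between arms is not the issue; the absolute proportions are.

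The eligibility condition in 4.4.1 is a separate, smaller matter. Vaccinated participants who do not meet the latest criteria drop out of the primary AE proportion. Their number and the direction of the effect are unknown.

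**What to change.** 1. In SAP 1.1, state that AE results in the Week 28-lock report are AEs through the data cut-off, give the distribution of follow-up with them, and say they are not the 72-week estimand. A label of AEs through Week 28 would be wrong unless later events were dropped, which would go against 4.4.2.
2. Assign the 72-week AE estimand, and the outcomes needing Week 52 or Week 72 visits (4.5.3, 4.5.4), to the analysis after the last Week 72 visit.
3. In 4.4.3, make the censored time-to-event estimate a commitment instead of an option. Have it cover participants still on study as well as those who discontinue. Use it for any 72-week AE risk quoted before Week 72 follow-up is complete, provided follow-up reaches Week 72.
4. Separately, in 4.4.1 define the safety set as everyone who received any study vaccination, regardless of eligibility.

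The cost is SAP wording only; design, sample size and efficacy tests are untouched. The 72-week results come later, AE onset dates are needed, the censored estimate is less precise at an early cut, and AE proportions may look slightly less favourable.
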